2.3. Secondary Objective(s) of the overall research program

• Identify the basic immune mechanisms which can explain the differences in the effects of OIT in desensitized vs. tolerant individuals.

• Determine whether immune monitoring measurements reflecting underlying mechanisms during OIT can be used to predict responses to OIT in individual subjects and, ultimately, to improve the safety and efficacy outcomes in peanut OIT protocols.

Figure 1: Study Design Part II: Randomization for Arm A,B,C* Sub-study GI Endoscopy -Baseline Peanut OIT (arms A and B)* Placebo (arm C)* (N=95) (N=25) Part III: Initial Dose Escalation Day Part III: Build up phase with every 2 Week Visits Dosing to 4g peanut protein maximum daily Sub-study GI Endoscopy Week 52 Part IV: Maintenance Every 13wk Visits (approximately Wks52—104) Dosing at 4g peanut protein daily. First on-study DBPCFC at 104wks. Then at week 104, do subjects meet criteria: 1) on OIT treatment for minimum 104 weeks, 2) taking daily maintenance dose of 4,000 mg protein for at least 13 weeks, 3) no severe reactions (Grade 3, Appendix 4 to home dosing from Week 92-Week 104, and/or 4) no reactions. (objective. Appendix 4) at the Week 104 DBPCFC? Sub-study GI Endoscopy YES Week 104 Part V: Tolerance and Desensitization testing phase every 13wk **Desensitization Failure** Visits (Wks117-156) Sub Study GI Endoscopy Week 117 At DBPCFC every 13wk visit, is there clinical reactivity on DBPCFC? If Arm B, Desensitization Failure YES NO, then continue part V If Arm A, Tolerance Failure

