3.1. Description of Study Design

A Phase 2, single-center, randomized double blind, placebo controlled study of the induction of peanut tolerance by oral immunotherapy (OIT). Our intent to treat population will be 120 subjects, ages 7-55 years, with an allergy to peanut, as determined by DBPCFC, history, clinical symptoms, and positive skin prick test (SPT). Please see Figure 1.

First, subjects will be screened (Part I, Figure 1). The 120 enrolled subjects will be randomized 2.4:1.4:1 (please see section 13). Thus, there will be three arms: (1) Arm A on peanut OIT until week 104 and once meeting criteria *[i.e. 1) on OIT treatment for minimum 104 weeks, 2) taking daily maintenance dose of 4,000 mg protein for at least 13 weeks, 3) no severe reactions (Grade 3, APPENDIX 4) to home dosing from Week 92-Week 104, and/or 4) no objective reactions, (Appendix 4) at the Week 104 DBPCFC]* has been assigned to avoid peanut (i.e. 600 mg oat flour). (2) Arm B on peanut OIT until week 104 and once meeting criteria, has been assigned to be maintained on 300 mg peanut protein (i.e. 600 mg oat flour). (3) Arm C that is maintained on placebo (oat flour) and once meeting criteria, will receive 600 mg oat flour beginning on week 104. This will be true even if a subject in the placebo group meets criteria at week 104. This way all participants will receive approximately the same volume of flour so that the subject blinding will be easier to maintain. The decision to maintain subjects on only 300 mg peanut protein after week 104 is for ease of eating peanut and to test if a lower amount of protein can still maintain desensitization. This upfront randomization is performed because our statistical analysis plan is focused on an intent to treat analysis.

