All arms will undergo an Initial Dose Escalation (IDE) Day and updosing regimen with a maintenance phase of OIT or placebo to a maximum of 4,000 mg protein daily, as peanut flour, in the OIT groups, and to a maximum of an equivalent amount of oat flour for the placebo group). (Part III, Figure 1). After maintenance is achieved, all subjects will begin performing DBPCFCs (staged so as to ensure safety) at Week 104 and every 13 weeks thereafter (Part IV, Figure 1). At Week 104, individuals that reach criteria (Part IV, Figure 1) will, based on the randomization that was done at the start of the study, either stop therapy with peanut and be switched to oat flour, or will be maintained on 300 mg peanut protein per day (Parts V, Figure 1). If subjects fail the week 104 DBPCFC they will not be given home doses. Those that fail the week 104 FC will remain in the study and return for a study completion visit at week 117 to meet the primary endpoint (will be analyzed in the intent to treat comparisons). All subjects will be evaluated every 13 weeks thereafter until the end of study.

Individuals in Arm A will be defined as "clinically tolerant" if there is no clinical reactivity at the Week 104 and Week 117 (or equivalent) DBPCFC. Clinical reactivity is defined as any objective reaction based on the Bock's Criteria (**Appendix 4**). Individuals in Arm A who meet the definition of "clinically tolerant" will continue to avoid peanut protein (i.e. continue on 600 mg per day of oat flour) as long as each subsequent DBPCFC (performed every 13 weeks until end of study) shows no clinical reactivity.

Individuals in Arm B will be defined as "desensitized" to a minimum of 300 mg per day of peanut protein if they show no clinical reactivity at DBPCFCs (week 117 (or equivalent) to end of study).

Individuals in Arm C will be defined as "natural loss of responsiveness" if they show no clinical reactivity at DBPCFCs (week 117 (or equivalent) to end of study).

We plan to identify the basic immune mechanisms which can explain the differences in the effects of OIT in individuals who do or do not become clinically tolerant and to determine whether immune monitoring can predict the safety and efficacy outcomes in peanut OIT protocols. After initial screening and enrollment, there are three phases of the study:

- Dose escalation and Build up Phase (Part III, Figure 1)
- Maintenance phase (Part IV, Figure 1)
- Tolerance and Desensitization Testing phase (Part V, Figure 1)

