After subjects have met the criteria outlined above (Section 3.1), medical history, diet history, spirometry, SPT, and a physical assessment will be performed. These subjects will be randomized 1:1 either to avoid OIT therapy (**see Figure 1**), and begin the avoidance phase, or they will be randomized to decrease their daily dose to 300 mg of peanut protein. After 3 months both arms will be re-challenged with 4,000 mg peanut protein, and then every 13 weeks for up to 4 additional OFCs. The placebo group may be unblinded to the research staff at week 117.

Peanut OIT:

Initial Dose Escalation Day (Day 0) – The Initial Dose Escalation (IDE) Day will be done at the CFRU and consist of peanut OIT dosing, beginning at 0.5 mg of peanut protein with graduated doses every 30 minutes up to 6 mg (see schedule for initial day dose escalation, **Table 1**). Subjects will not have active wheezing, spirometry demonstrating FEV1 <80% predicted, or a current flare of atopic dermatitis that contraindicates dosing in the clinical judgment of the study physician. A physician will be present at all times during any of the CFRU peanut OIT dosing visits and will be available to respond within 60 seconds to any allergic reaction. Subjects tolerating the 6 mg single dose will remain on that daily dose for 2 weeks. They will then return every 2 weeks to the CFRU for single updose. Subjects who do not tolerate the 1.5 mg dose will be considered treatment failures and will not initiate home dosing.

Table 1: Peanut Protein or Placebo (oat protein)Dosage Escalation Schedule on the Initial Dose Escalation Day

Dose #	Peanut Dose	Cumulative Peanut Dose	
1	0.5 mg	0.5 mg	
2	0.8 mg	1.3 mg	
3	1.5 mg	2.8 mg	
4	3.0 mg	5.8 mg	

5 6.0 mg 11.8 mg

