The subject's sensitivity to peanut allergen is defined as the dose at which the subject experiences allergic reactions. All symptoms and signs will be evaluated and rated based on a standardized oral food challenge scoring system (Appendix 4).

During the oral food challenge, there should be increased hydration (i.e. about 16 oz or more orally).

Updosing during the DBPCFC will be stopped when the Principal Investigator (or designee) finds symptoms and/or signs that indicate a definite allergic reaction (Bock scoring system (objective, **Appendix 4**) has occurred based on clinically significant changes in reported symptoms, physical findings, or vital signs that the subject is experiencing to the challenge material. The challenge will consist of 7 doses (peanut or placebo), given about every 15-30 minutes for lower doses and about every 45 minutes or longer for higher doses (in bold): 5 mg, 50 mg, 220 mg, **625 mg, 1,000 mg, and 1,050 mg and 1,050 mg** (4,000 mg protein total). The doses for DBPCFCs conducted on or after Week 104 in this
protocol were selected with the rationale that some study subjects will be receiving placebo and would be expected to maintain the same level of sensitivity displayed at the screening DBPCFC to a cumulative dose of 500 mg of peanut protein. Both peanut and oat protein will be concealed in a food that masks the taste. After the last dose of the DBPCFC, the subject will be monitored for 2 hours and then discharged home. Subjects will be considered to have tolerated the OFC if they do not experience any objective reactions by Bock's Criteria (**Appendix 4**).

If the subject experiences reactions, they will be treated with the necessary rescue medications. They will be observed for a minimum two hours after the final administered dose and discharged home only when deemed clinically stable by a study physician.

After the Week 104 DBPCFC, subjects who meet the following criteria will reduce their daily maintenance dose to 300 mg peanut protein daily or to discontinue peanut protein daily dosing entirely (i.e., switch to 600mg oat flour):

- On OIT treatment for minimum 104 weeks,
- Taking daily maintenance dose of 4,000 mg protein for at least 3 months,
- No severe reactions (Bock's Criteria Grade 3, APPENDIX 4) to home dosing from Week 92-Week 104, and/or
- No objective reactions by Bock's Criteria, Appendix 4 at the DBPCFC at Week 104

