8.4.1. Unscheduled Visits

If disease activity increases or other concerns arise between regularly scheduled visits, participants should be instructed to contact study personnel and may be asked to return to the study site for an "unscheduled" visit.

Unscheduled visits may be performed for significant food allergy episodes which may be reported by the subject between regularly scheduled visits. Significant food allergy episodes are defined as those for which epinephrine is administered based on criteria in the subject's Food Allergy Action Plan. Unscheduled visits may include physical assessment, blood draw and/or skin prick test. Review of the circumstances around the episode and appropriate documentation of the adverse event will be recorded in the study chart.

Visit Windows

Table 3: Visit Windows

Visit Type	Target Date	Visit Window			
Screening/Baseline/Randomization	Day -300 to 0	Day -300 to 0			
Initial Dose Escalation Day	Day 0	Day 0 (by definition)			
Dose Escalation Phase	Weeks 2, 4, 6, 8 until maintenance				
Dose Escalation Phase	dose is reached]	±14 days			
Maintenance Phase	Weeks 52, 65, 78, 91, and 104				
Telerance Dhace	Weeks 117 (or equivalent), 130, 143,				
	and 156				

9. Mechanistic Assays

Comparisons for each of the parameters discussed below could occur between:

- Treatment vs. Placebo group, and
- On Treatment vs. Baseline for each subject, and
- Tolerant vs. Desensitized vs. Refractory (those that terminate early due to not being able to be desensitized) clinical outcomes

I) Serum Assays

Table 4: Serum Assays

Panel	Volume needed for each sample collection
Specific IgE, IgG4, IgA anti-peanut and the component-resolved (presume IgE and IgG4 anti-Ara h 1,2,3,6,8)	1 ml
Epitope Array Peanut	350 microliters

Table 5: Expected Results for Serum Parameters

Parameter	On Therapy	Tolerance	Desensitization	Refractory
Specific IgE And Specific IgG4	Progressive decrease in specific IgE to peanut and increase in specific IgG4	Low specific IgE and increased IgG4 which persists despite the 3 month period of abstinence	Low specific IgE and increased IgG4 which reverses in the 3 month period of abstinence	No change in specific IgG4 to peanut
Epitope Array for IgE for peanut	Progressive Inhibitory antibodies	Lowest epitope spreading at	Intermediate epitope spreading at	Highest epitope spreading at baseline predicts

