13.1 Overview

This double blind, randomized, placebo controlled study in peanut-allergic children and adults intends to identify basic immune mechanisms that explain the effects of OIT in individuals who do or do not become clinically tolerant and to determine whether immune monitoring can predict safety and outcomes in OIT protocols.

The 120 enrolled subjects will be randomized 2.4:1.4:1. Thus, there will be three arms: (1) Arm A (60 subjects) on peanut OIT until week 104 and once meeting criteria [*i.e.* 1) assigned to OIT treatment for minimum 104 weeks, 2) reaching maintenance 13 weeks prior to DBPCFC at week 104 3) no severe reactions (Grade 3, APPENDIX 4) to home dosing from Week 92-Week 104, and/or 4) no objective reactions, (Appendix 4) at the Week 104 DBPCFC] has been assigned to avoid peanut (i.e. 600 mg oat flour). (2) Arm B (35 subjects) on peanut OIT until week 104 and once meeting criteria, has been assigned to be maintained on 300 mg peanut protein (i.e. 600 mg peanut flour). (3) Arm C (25 subjects) that is maintained on placebo (oat flour) and once meeting criteria, will receive 600 mg oat flour beginning on week 104. This will be true even if a subject in the placebo group meets criteria at week 104. This way all participants will receive approximately the same volume of flour so that the subject blinding will be easier to maintain. The decision to maintain subjects on only 300 mg peanut protein after week 104 is for ease of eating peanut for so long. This upfront randomization is performed because our statistical analysis plan is focused on intent-to-treat principles.

The primary analysis is an intent-to-treat comparison of success rates between arms A and C, where success is defined by reaching and passing the DBPCFC at both 104 weeks and 117 (or equivalent) weeks.

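### Section 8.3 orders a 1:1 randomisation of subjects who meet the Week 104 criteria, contradicting the single upfront 60:35:25 randomisation on which the primary analysis rests

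*Protocol*

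**What the plan says.** In Section 8.3, under the Peanut OIT Treatment Overview, the protocol takes subjects who have met the Section 3.1 criteria and states: "These subjects will be randomized 1:1 either to avoid OIT therapy" or to a reduced daily dose of 300 mg peanut protein. The next sentence keeps the same two-arm picture: "After 3 months both arms will be re-challenged with 4,000 mg peanut protein".

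The design is described differently elsewhere:

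- **Figure 1** places "Part II: Randomization for Arm A,B,C" before the Initial Dose Escalation Day.
- **Section 3.1** states "The 120 enrolled subjects will be randomized 2.4:1.4:1 (please see section 13", and has subjects who reach the criteria at Week 104 switched "based on the randomization that was done at the start of the study".
- **Section 13.1** gives arm sizes of 60 (A), 35 (B) and 25 (C), and the reason: "This upfront randomization is performed because our statistical analysis plan is focused on intent-to-treat principles".
- **Table 3 (Visit Windows)** lists "Screening/Baseline/Randomization" as one visit type, in the window Day -300 to 0.
- **The Week 104 visit text in Section 8.3** says "subjects who meet the following criteria will reduce their daily maintenance dose to 300 mg peanut protein daily" or stop peanut dosing. It orders no new randomisation.

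The analysis rules build on the upfront version. Section 13.4.1 defines the ITT sample as everyone randomised. Section 13.4.2 counts an unevaluable test as a failure. Section 13.7 keeps all subjects randomised to A or C in the primary analysis, with drop-outs counted as failures. Section 8.3 also keeps those who miss the Week 104 criteria in the intent-to-treat analyses.

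**The concern.** The protocol carries two randomisation instructions, and the deviant one sits in the section that describes study procedures. It cannot be read as loose wording for the baseline assignment, because it places the act after the criteria are met and gives a different ratio.

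The primary comparison is arm A against arm C. Counting early failures and drop-outs in arm A requires every peanut subject to carry an A or B label from baseline. If that label were issued only to subjects who qualify at Week 104, those who failed or left earlier would belong to neither arm and would fall out of the arm A denominator. Arm A would then hold only subjects who had already met the Week 104 criteria, while arm C would still hold everyone assigned to placebo. That bias favours OIT, and it is what the upfront randomisation is meant to prevent.

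**Working it through.** **1. Does the stated allocation give the stated sizes?** Inputs: N = 120 and ratio 2.4:1.4:1 (Sections 3.1 and 13.1). The ratio sums to 4.8.

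- A: 120 × 2.4/4.8 = 60
- B: 120 × 1.4/4.8 = 35
- C: 120 × 1/4.8 = 25

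These match Section 13.1. Peanut subjects total 60 + 35 = 95, and A:B = 60/35 ≈ 1.71:1, not 1:1.

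**2. Does the stated power hold for the upfront design?** Inputs from Section 13.7: success rates 0.35 (A) and 0.05 (C), two-sided alpha 0.05, n = 60 and 25. Normal approximation with pooled variance under the null:

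power = Φ{ [ |p₁ − p₂| − 1.96 √( p̄(1 − p̄)(1/n₁ + 1/n₂) ) ] / √( p₁(1 − p₁)/n₁ + p₂(1 − p₂)/n₂ ) }

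- p̄ = (60 × 0.35 + 25 × 0.05)/85 = 22.25/85 = 0.2618
- Null standard error = √(0.1932 × 0.05667) = 0.1046; × 1.96 = 0.2051
- Alternative standard error = √(0.2275/60 + 0.0475/25) = 0.0754
- power = Φ((0.30 − 0.2051)/0.0754) = Φ(1.258) = 0.896

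This agrees with the stated 90%. The same formula at 60 and 25 reproduces all 15 cells of the Section 13.7 table after rounding.

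**3. Can a 1:1 split deliver the planned arm A?** An even split of 95 gives 47 and 48, so arm A is at least 60 − 48 = 12 subjects short (12/60 = 20%). To reach 60 at 1:1 would need 2 × 60 = 120 peanut subjects; there are 95.

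**4. What if only qualifying subjects are split?** The protocol does not state the share expected to meet the criteria, so the shares below 100% are assumptions for illustration.

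| Share qualifying | Qualify | Arm A at 1:1 | Shortfall from 60 | Peanut subjects with no A or B label |
|---|---|---|---|---|
| 100% | 95 | 47 or 48 | 13 or 12 (22% or 20%) | 0 |
| 80% (assumed) | 76 | 38 | 22 (37%) | 19 |
| 60% (assumed) | 57 | 28 or 29 | 32 or 31 (53% or 52%) | 38 |

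The rows are alternatives and are not to be added together.

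**5. Power if 8.3 were followed.** In the 100% row no one is selected out, so 0.35 against 0.05 still applies. The formula in step 2 gives 0.869 for 48 and 25, and 0.866 for 47 and 25, which is about 87%. In the other rows the success rate among qualifying subjects would not be the all-randomised rate of 0.35, so a power figure would mislead. The protocol gives no basis for sizing the selection bias, and none is offered.

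**6. The texts side by side.**

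| | Upfront text | Section 8.3 overview |
|---|---|---|
| Timing | Baseline, by Day 0 | After the criteria are met |
| Ratio A:B | 60:35 | 1:1 |
| Population | All 120 enrolled | Peanut subjects meeting the criteria |

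**The case against.** The best reply is that the protocol already answers the question. Sections 3.1 and 13.1, Figure 1 and Table 3 agree on one baseline randomisation. Section 3.1 says outright that the Week 104 step follows it, and the detailed Week 104 instructions do not re-randomise. The lists are held by unblinded pharmacists, so every subject should have an arm before Day 0. On that view early failures already sit in A or B, and the harm needs staff to follow one overview sentence against everything else. This stands as a limit on how likely the harm is, and the upfront text should be taken as governing. It does not remove the contradiction: Section 8.3 is current procedural text and orders a randomisation the design does not contain.

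It is also fair to say that the 80% and 60% shares are not the protocol's, and that the ceiling of 48 presumes an even split. Both are labelled so here, and the contradiction depends on neither.

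A third reply is that the reference to both arms naturally means the two peanut arms, since the placebo group is dealt with separately straight afterwards. That reading works today, but the phrase takes its meaning from the 1:1 sentence and needs a new referent once that sentence goes.

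Finally, the two-by-two block description in Section 3.4 is a separate matter. It does not visibly fit three arms at 2.4:1.4:1, but block details may properly live in a randomisation specification. It is noted as secondary and carries no weight in the conclusion.

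**Conclusion.** The concern holds: the 1:1 sentence in Section 8.3 is wrong as written. It conflicts with the rest of the protocol on timing, ratio and population, and the two versions cannot both be carried out. This is an internal contradiction, not a flaw in the upfront design, whose 60:35:25 allocation and 90% power are both correct.

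If the sentence were followed with an even split, arm A would be at least 12 subjects (20%) short of plan. Power would be about 87% in the one case without selection, where all 95 peanut subjects qualify. With fewer qualifying, the more serious consequence is that early failures and drop-outs lose their place in arm A, so the ITT and drop-outs-as-failures rules cannot be applied to it. The direction of that bias is clear; its size is not estimable from the protocol. The point should be fixed, and confidence in it is high.

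**What to change.** In the Section 8.3 Treatment Overview, replace the 1:1 sentence with: *Subjects who meet the Week 104 criteria proceed according to the arm assigned at the baseline randomization; no further randomization takes place.* Reword the sentence that follows so that it refers to the baseline arms, consistent with the Week 117 to 156 text in the same section, which names the 300 mg, avoidance and qualifying placebo subjects.

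As a secondary tidy-up, the sponsor should reconcile the block description in Section 3.4 with the three-arm baseline allocation, leaving block details to the randomisation specification.

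The cost is two sentences in Section 8.3 and one clarified phrase in Section 3.4. Arm sizes, power, participants and procedures are unchanged.

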As stated above, an updosing attempt must be made within 3 clinic visits on a given dose, unless updosing is delayed due to administration of epinephrine as defined in Section 7.4 or illness. If the subject fails to successfully increase updosing for three consecutive attempts, updosing will be halted at the last tolerated dose and the subject will continue on that dose as their maintenance dose for the remainder of the study. The subject will be followed for the remainder of the study for safety and immunologic monitoring.

Vigorous exercise is not permitted for at least 2 hours after the dose of oral allergen immunotherapy. Also, there must be at least 1 hour between vigorous exercise and taking a dose of oral allergen immunotherapy. Allergic reactions are still possible when exercise takes place more than 2 hours after the dose.

Should significant systemic symptoms, which may include mild symptoms based on physician discretion or moderate or greater symptoms, be reported during the daily home dosing, the symptom/dosing algorithm will be followed to determine the best course of action. The appropriate treatment will depend on the type and number of symptoms. Subjects will be allowed to take their other daily medications during the build-up and maintenance phases of the study (i.e., antihistamines, albuterol) except where prohibited in this protocol.

Every 13 weeks during the build-up phase, subjects will have blood drawn for mechanistic labs, including basophil activation studies and pregnancy testing, if applicable. Blood will be collected prior to attempted dose escalations, but the decision to updose will be made based on clinical parameters, not the results of the assays.

Weeks 52, 65, 78, and 91– Maintenance Phase

Subjects will undergo updosing until reaching a daily maintenance dose of 4,000 mg and they will remain at that dose and return for follow-up visits at Weeks 52, 65, 78, and 91. Each of these visits will include a physical assessment, spirometry, skin test, and blood draw for mechanistic studies. Based on our previous data using a similar dosing method (Table 2), we expect all subjects on active treatment to reach 4,000 mg between the Week 44 and Week 78 visits.

Week 104 - On Study DBPCFC (to 4,000 mg)

At Week 104 all subjects will have a DBPCFC to 4,000 mg (as per staged challenge above) to assess desensitization. The visit will also include a physical assessment, spirometry, skin prick test and blood draw for mechanistic studies.

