Subjects who do not meet these criteria at Week 104 will be considered desensitization failures and will be offered a follow-up protocol that is separate from this protocol once they reach the primary endpoint. They will be considered in statistical analyses of the intent-to-treat population.

After Week 104, double blinding will continue by using the same quantity of flour for all groups (600 mg total of oat flour daily for placebo group and 600 mg total of oat flour daily for avoidance group; approximately 600 mg total of peanut flour --to provide exactly 300 mg peanut protein—for the 300 mg peanut protein group).

Separate GI Sub Study.

Subjects will undergo the second endoscopy at week 52, and a third endoscopy at week 104 and a fourth endoscopy at week 117 (or equivalent). These will be performed by a board certified gastroenterologist at Stanford Endoscopy suite. This will be performed under mild anesthesia using fentanyl, versed and midazolam and subjects will be observed in the endoscopy recovery room per standard of care. Biopsies will be taken from the esophagus, stomach and duodenum.

Weeks 117 (or equivalent), 130, 143, and 156 - On Study DBPCFC (to 4,000 mg)

At Weeks 117 (or equivalent), 130, 143, and 156, subjects will have a DBPCFC to 4,000 mg (as per staged challenge above) to assess tolerance. Subjects who fail these challenges (i.e., who exhibit objective reactions by Bock's Criteria, **Appendix 4**) will be offered a follow-up protocol that is separate from this protocol.

Subjects who are randomized either to 300 mg peanut protein or peanut avoidance or the placebo subjects who pass the week 104 criteria will return to CFRU at Weeks 117 (or equivalent), 130, 143, and 156. Each of these visits will include a physical assessment, spirometry, skin test, blood draw for mechanistic studies, and a DBPCFC to 4,000 mg as outlined above to assess clinical reactivity.

During the oral food challenge, there should be increased hydration (i.e. about 16 oz or more given orally).

There are no data indicating that repeating food challenges every 3 months will or will not induce desensitization or otherwise affect the outcomes in this study. Our preliminary studies in which we have performed DBPCFCs every 3 months in a separate phase 1 study cohort (n=87 subjects) have demonstrated no increased risk of sensitization.

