Appendix 1: Schedule of Events

*Initial Dose Escalation Day

Informed consent obtained prior to completion of any study procedures ^Subjects return for up-dosing every 2 weeks. Blood to be obtained every 12 weeks *Urine pregnancy test to be performed preferentially. Serum pregnancy test to be performed to confirm positive urine results, if any.

****Week number may be + or -2 weeks.

Study Stage		Buil	d-up F	hase	(Weeł	(#)				Main	tenan	ce Pha	ise						Early Completion
Time	Week****	30	32	34	36	38	40	42	44	52	65	78	91	104	117	130	143	156	Withdrawal/
															^				Early Termination
	Visit #	15	16	17	18	19	20	21	22	23	24	25	26	27	28	29	30	31	
Informed Consent*	**																		
Medical History																			
Physical Exam		Х	Х	Х	Х	Х	Х	Х	Х	Х	Х	Х	Х	Х	Х	Х	Х	Х	X
Concomitant Medi	ications	Х	Х	Х	Х	Х	Х	Х	Х	Х	Х	Х	Х	Х	Х	Х	Х	Х	Х
Adverse Events		Х	Х	Х	Х	Х	Х	Х	Х	Х	Х	Х	Х	Х	Х	Х	Х	Х	X
Peanut/Placebo Do	osing	Х	Х	Х	Х	Х	Х	Х	Х										
Total IgE										Х	Х	Х	Х	Х	Х	Х	Х	Х	Х
Peanut Specific IgE	and IgG4									Х	Х	Х	Х	Х	Х	Х	Х	Х	Х
Peanut skin testing	5									Х	Х	Х	Х	Х	Х	Х	Х	Х	X
CBC with differenti	ial									Х	Х	Х	Х	Х	Х	Х	Х	Х	Х
Mechanistic labs					Х					Х	Х	Х	Х	Х	Х	Х	Х	Х	Х
Serum or urine pre	egnancy***									Х		Х		Х		Х		Х	
Spirometry		Х	Х	Х	Х	Х	Х	Х	Х	Х	Х	Х	Х	Х	Х	Х	Х	Х	X
Screening DBPCFC																			
On-Study DBPCFC ⁺														Х	Х	Х	Х	Х	
Diaries		Х	Х	Х	Х	Х	Х	Х	Х	Х	Х	Х	Х	Х	Х	Х	Х	Х	Х
EpiPen [®] Training																			

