Appendix 1 (cont'd)

[†]First On-study DBPCFC to 4,000 mg performed at Week 104 in all subjects. Participants meeting criteria at week 104 (Part IV, Figure 1) may also have DBPCFCs at Weeks 117 (or equivalent), 130, 143, and 156.

^ Possible early completion visit for those participants who demonstrate objective allergic reactions (Appendix 4) at week 104 DBPCFC.

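### No same-visit pregnancy test at the Week 117 and Week 143 peanut challenges, and no stated rule that pregnancy cancels a challenge

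*Protocol*

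**What the plan says.** **Challenges.** Section 8.3 sets the first on-study challenge: "At Week 104 all subjects will have a DBPCFC to 4,000 mg (as per staged challenge above) to assess desensitization". The Appendix 1 footnote agrees: "First On-study DBPCFC to 4,000 mg performed at Week 104 in all subjects". Section 3.1 words it as "After maintenance is achieved, all subjects will begin performing DBPCFCs". For subjects who meet the Week 104 criteria, section 8.3 describes Weeks 117, 130, 143 and 156 as follows: "Each of these visits will include a physical assessment, spirometry, skin test, blood draw for mechanistic studies, and a DBPCFC to 4,000 mg". The Appendix 1 footnote is softer for these visits: such participants "may also have DBPCFCs at Weeks 117 (or equivalent), 130, 143, and 156".

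**Pregnancy tests.** The Appendix 1 row is marked at screening and at Weeks 24, 52, 78, 104, 130 and 156. Its footnote reads "Urine pregnancy test to be performed preferentially", with serum to confirm a positive result. The one sentence on testing in the visit text of section 8.3 covers build-up only: "Every 13 weeks during the build-up phase, subjects will have blood drawn for mechanistic labs, including basophil activation studies and pregnancy testing, if applicable".

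**What pregnancy triggers.** Section 4.3 (item 14) excludes pregnancy at entry. Section 12.6 requires a pregnant subject to stop study medication. Section 6.5 allows therapy to be stopped, and section 11.2 (item 5g.iii) allows the participant to be terminated. Both of these are permissive. Section 12.2.1 places challenge material outside the definition of study drug.

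**The concern.** A 4,000 mg challenge is a deliberate exposure to the allergen, and section 5.2 accepts that reactions to challenges can be life-threatening. The sponsor already treats pregnancy as a bar to entry and a reason to stop dosing, and pairs a test with the challenge at three of the five visits. At the other two it does not. One of these is the primary-endpoint visit, when Arm A has been off peanut for three months.

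There is also a gap in the rule. Even where a test is done, the protocol does not say what a positive result means for that day's challenge. The only mandatory instruction concerns study medication, and challenge material is defined as something else. At stake is the safety of a very small number of subjects, and clear instructions for the site.

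**Working it through.** **Step 1: align the Appendix 1 rows from Week 104.** The footnote "Week number may be + or -2 weeks" gives the window used in the last column.

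| Week | 4,000 mg challenge | Pregnancy test | Nominal weeks since last scheduled test | Longest, with windows |
|---|---|---|---|---|
| 104 | yes | yes | 0 | same visit |
| 117 | yes | no | 117 − 104 = 13 | (117 + 2) − (104 − 2) = 17 |
| 130 | yes | yes | 0 | same visit |
| 143 | yes | no | 143 − 130 = 13 | (143 + 2) − (130 − 2) = 17 |
| 156 | yes | yes | 0 | same visit |

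Three of five challenges have a same-visit test. Neither the section 8.3 visit list nor the 13-weekly build-up sentence supplies the other two.

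**Step 2: look for a rule that withholds the challenge.**
- Section 12.6 is mandatory but reaches study medication only, and section 12.2.1 takes challenge material out of that category.
- Sections 6.5 and 11.2 are permissive.
- Section 11.4 describes visits after stopping treatment as a skin test and a blood draw, and the early-termination column of Appendix 1 marks no challenge. Both imply that there is no challenge, but neither says so.
- Section 8.3 and the Appendix 1 footnote give the Week 104 challenge to all subjects without exception.

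No stated rule cancels a challenge for pregnancy.

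**Step 3: size.** The protocol gives no pregnancy rate and no number of subjects of child-bearing potential. As an assumption, take 10–30% of subjects as of child-bearing potential and 1–5% pregnancies a year under the birth control that section 4.2 (item 10) requires. The interval is 13/52 = 0.25 year.

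Expected pregnancies between the Week 104 test and the Week 117 challenge, if all 120 subjects were still being challenged:
- low: 120 × 0.10 × 0.01 × 0.25 = 0.03
- high: 120 × 0.30 × 0.05 × 0.25 = 0.45

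This is a ceiling under these rates, because only subjects who meet the Week 104 criteria go on, and some pregnancies would be known without a scheduled test. The same ceiling applies to Weeks 130–143.

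**The case against.** The best defence is that the protocol is not silent. A test is scheduled 13 weeks before each of the two challenges, birth control is required throughout, and sections 6.5, 11.2 and 11.4 together give a pregnant subject a way out of dosing and into follow-up without a challenge. Section 11.2 (item 4) also lets the investigator end participation in the subject's interest. On this view, a test at every challenge is a preference about frequency.

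Most of that is fair, and it limits the point. It does not remove it. Each way out depends on the pregnancy being known, and a test up to 17 weeks old cannot show status on the day. The ways out also remain a matter of inference and discretion.

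A reader might infer more than the document supports:
- **That testing becomes less frequent in the challenge phase.** The build-up text speaks of every 13 weeks, but Appendix 1 runs 24, 52, 78, 104, 130, 156, so the interval is 26 to 28 weeks from Week 24 on. By the schedule, nothing falls.
- **That section 5.2 means subjects stopped for hypotensive anaphylaxis are challenged again with an IV catheter in place.** Exclusion 16 in section 4.3 concerns anaphylaxis to peanut, while the catheter sentence names no allergen. A subject with such a reaction to another food could enrol, so the sentence has an ordinary use.
- **That subjects stopped for hypotensive anaphylaxis are left unprotected.** Sections 6.4, 11.2 and 11.4 largely cover them. The criterion of 104 weeks on treatment keeps those stopped earlier out of the later challenges, subject to the loose and/or in that list.
- **That sections 6.5 and 11.2 conflict.** Both are permissive and can be followed together.

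**Conclusion.** The point holds as a minor patient-safety improvement. Two of the five 4,000 mg challenges, including the primary-endpoint one, have no same-visit pregnancy test, and no stated rule cancels a challenge for pregnancy at any of the five. These facts come directly from the document and need no assumption.

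The expected number of subjects is very small: 0.03 to 0.45 at Week 117 as a ceiling, resting wholly on the assumed rates. A reader might also infer a threat to the primary result. The document does not support that, because the gap as written does not alter the primary comparison. A lost Week 117 result would arise only from the remedy.

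**What to change.** 1. In Appendix 1 and section 8.3, add a pregnancy test before the Week 117 and Week 143 challenges for subjects of child-bearing potential. Urine is enough, or serum from the blood already drawn at both visits.
2. In sections 8.3 and 12.6, state that a positive test cancels the challenge, including at Week 104.
3. Optionally, add one clause that subjects stopped for peanut-induced hypotensive anaphylaxis are followed under section 11.4 without a challenge.

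**Cost.** One extra test at two visits and a few short edits, with no added subjects and no new analysis rule. A Week 117 challenge cancelled for pregnancy counts as a failure under section 13.4.2. Under the same assumed rates, Arm A pregnancies in that interval number 60 × 0.10 × 0.01 × 0.25 = 0.015 to 60 × 0.30 × 0.05 × 0.25 = 0.225. Multiplied by the planned success rate of 0.35 (section 13.7), the expected loss is 0.005 to 0.08 successes out of a planned 60 × 0.35 = 21. That is an acceptable price.
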